visible at the time of surgery even after neoadjuvant chemotherapy (lag time) and is the status of sentinel and tattooed lymph nodes predictive of the axillary nodal status.

Study Objectives

Primary Outcomes

- Intra-operative identification of tattooed lymph node(s) in upfront surgery group (Phase I)
- Intra-operative identification of tattooed lymph node(s) in the post-neoadjuvant surgery group (Phase II)

Secondary Outcome

- Concordance rate between identified sentinel node(s) and tattooed lymph node(s)

Methodology

Study Design

A quasi-experimental pilot study will be conducted to evaluate the feasibility of tattooing suspicious lymph nodes with sterile black India Ink in breast cancer patients. Patients with suspected (who have not had a breast biopsy yet but clinically are suspected to have breast cancer) or biopsy proven breast cancer, with clinically suspicious axillary nodes, who have not had axillary lymph node biopsy yet, will be considered for this study. Such patients will then undergo an ultrasound guided core needle biopsy of the breast (if not already done) as well as of the suspicious axillary lymph node, in the radiology department by study radiologists as per our current institutional protocol. For the purpose of the study, at the time of the lymph node core biopsy, the biopsied node will be tattooed by injecting 0.1-0.5 ml (larger lymph nodes will be injected with more ink) of sterile black India ink.

In the first phase, 10 patients planned for upfront surgery will be included. This part of the study will help to evaluate whether black India ink (injected percutaneously into the lymph node at the time of percutaneous axillary biopsy) can be identified intraoperatively by the surgeon and does it help in retrieval of this percutaneously biopsied lymph node. All lymph nodes excised including sentinel, tattooed (if recovered) and non-sentinel will be submitted in separately labelled containers for further

pathologic evaluation. Determination of concordance between sentinel and tattooed nodes, will be primarily done visually by the surgeon and confirmed by 2 independent pathologists, blinded to each other's findings. Pathologic evaluation will determine concordance between sentinel/tattooed and non-sentinel nodes.

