In Phase 2, we will perform the same procedure as detailed above (percutaneous lymph node biopsy and tattooing of lymph node with black India Ink) on 30 patients who are planned to undergo neoadjuvant chemotherapy. Chemotherapy typically is administered over 4-6 months, which leads to a lag time between percutaneous lymph node biopsy/tattooing and surgery. We will need to determine whether the tattoo on the lymph node remains intraoperatively visible and retrievable despite the lag of several months (while undergoing neoadjuvant chemotherapy). Pathologic evaluation will determine concordance between sentinel/tattooed and non-sentinel nodes.

Clinical stage and evaluation by the surgeon as well as patient preference will determine the timing of surgery, upfront or after NCT. In all cases, whether pathologically negative or positive on biopsy, a SLNB will be performed at the time of definitive surgery, with dual tracer technique using technitium-99 sulfur colloid and methylene blue as per current institutional protocol. Intraoperatively, the axilla will be inspected to determine whether the black India ink tattooed in the lymph nodes can be visualized or not, is it easily distinguishable from methylene blue and is the tattooed lymph node also the SLN. In cases where biopsy of lymph node was negative, an intraoperative frozen section will be performed on the retrieved lymph nodes (SLN and tattooed) and need for ALND will be determined according to current institutional protocol. All those with evidence of metastatic disease on previous core biopsy or on frozen section of SLN/tattooed LN will then proceed to have an ALND. All lymph nodes i.e. sentinel, tattooed and non-sentinel (retrieved in ALND) submitted will be processed and evaluated as per routine protocol by a single study pathologist, who will issue the final pathology report. The additional study part will require evaluation of methylene blue and India Ink tattoo by the second independent study pathologist, to see if the two are grossly and/or microscopically distinguishable. Both pathologists will be blinded to each

other's findings. This additional evaluation will not affect the pathologic stage or further treatment decisions. This step/part of the study could however impact future surgical technique.

Study Setting

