The study will be conducted at Department of Surgery in collaboration with Department of Pathology and Radiology, the Aga Khan University Hospital Karachi-Pakistan (AKUH). AKUH is a Joint Commission International Accreditation (JCIA) accredited hospital and is one of the biggest private tertiary care hospitals in Karachi. The multidisciplinary AKUH breast surgery team consists of well qualified breast surgeons, radiologists, medical oncologists and pathologists who provide evidence based standard care to breast cancer patients following strict adherence to institutional guidelines. The reason for conducting single center study is to limit variability in management of breast cancer patients at different centers as AKUH provides a non-biased, controlled environment to evaluate the feasibility of injecting sterile black India ink and subsequently retrieval of the SLN using dual tracer technique, with attempted identification and retrieval of the marked/tattooed lymph node.

Study Participants

Women greater than 18 years old with histologically confirmed diagnosis of breast cancer or clinically suspected breast cancer and clinically suspicious ipsilateral axillary lymph nodes (on clinical exam or ultrasound) presenting to AKUH fulfilling our eligibility criteria and willing to give written informed consent for the whole duration of study period will be recruited.

Eligibility Criteria

Inclusion Criteria

- ✚ Female greater than 18 year of age

- ✦ Breast cancer patient (biopsy proven or clinically suspected) with clinically suspicious (palpable on clinical exam or abnormal by ultrasound criteria but not biopsied yet) ipsilateral axillary lymph node(s). The ultrasonographic examination will be considered suspicious for metastasis if one or more of following criteria are present: 1. Eccentric cortical enlargement (>3 mm) or lobulation with displacement of hilum 2. Absent hilum and irregular border and hypoechoic echotexture 3. Spherical node 4. Perinodal vascularity. (18-20)
- ✦ Participants willing to undergo axillary lymph node percutaneous biopsy with marking/tattooing of the biopsied lymph node at Aga Khan University Hospital
- ✦ Participants intending to have definitive surgery at Aga Khan University Hospital

Exclusion Criteria

- ✦ Participants with terminal disease like renal failure will be excluded because these conditions can have profound effect on their course of treatment
- ✦ Participants with distant metastases

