Participants as per the institutional guidelines will undergo the routine clinical breast examination by trained specialist breast surgeon and radiological investigation. Those with suspected or histologically confirmed breast cancer and suspicious (but not biopsied yet) ipsilateral axillary lymph nodes on clinical exam or ultrasound will undergo an ultrasound guided core needle biopsy of the breast as well as the single, most

suspicious axillary lymph node either concurrently with core biopsy of the breast or in addition to previously performed core needle biopsy of breast, in the radiology department by study radiologists.

The biopsied lymph nodes will be tattooed with sterile black India ink immediately following sampling of the suspicious lymph node. Those planned for upfront surgery (Phase I) will be prepared and consented for surgery. Those planned for NCT (Phase II) will receive NCT followed by definitive surgery after completion of chemotherapy.

All study patients will have a sentinel lymph node biopsy and frozen section on retrieved SLN as part of axillary surgery. For this purpose after injection of TC⁹⁹ and lymphatic mapping preoperatively, diluted methylene blue will be injected into the subareolar plexus intraoperatively. The axillary hot spot will be assessed and documented for presence or absence, using a gamma probe. Intraoperatively axilla will be inspected to determine whether sterile black India ink tattooed in the lymph nodes is visible or not. Sentinel lymph node biopsy will be performed in usual fashion including identification of palpable lymph nodes. Total number of sentinel lymph nodes retrieved, number of hot, number of blue and number of hot and blue will be documented. If the sentinel node is also the marked/tattooed node it will be assessed and documented.

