Subsequently, those with a biopsy proven axillary metastatic disease on axillary core needle biopsy (regardless of frozen section results), will proceed to have the planned breast procedure and axillary lymph node dissection levels I and II in usual fashion. Management of axilla in those participants who did not have biopsy proven metastatic disease on axillary core needle biopsy (but had a suspicious node leading to core biopsy), will be dictated by results of frozen section analysis. If the frozen section results show absence of metastatic disease in the submitted lymph nodes, no additional axillary surgery will be performed. While the frozen section is in process and results are awaited, the surgeon may proceed with the planned breast procedure. ALND will be followed by placement of a drain in the axilla as per routine. For post NCT patients, extent of fibrosis (mild, moderate or severe) will be documented. All submitted lymph nodes will be evaluated by two independent pathologists to ascertain the visualization of sterile black

India ink within the nodes, and usual histologic assessment of all submitted specimens. Correlation between, marked/tattooed and sentinel nodes (including palpable) will be determined. Tumor pathology, including type, grade, receptors (ER, PR and Her-2/neu) will be reported. Credentialed surgeon, radiologists and pathologists according to institutional guidelines will participate in the study as this will lead to minimization of experimenter/assessor bias. (Study Flow Diagram)

Statistical Analysis

Analysis will be performed in Stata version 12. Descriptive analysis will be performed. For continuous variables either Mean \pm S.D or Median with IQR will be reported depending on the normality assumption of the variables. For categorical variables frequency with percentages will be reported. Proportion of lymph node visualized intraoperatively with Black India Ink will be reported. Concordance between the sentinel lymph nodes and tattooed biopsied lymph nodes will be reported. False negative rate (FNR) will be determined to assess the findings of preoperative pathological assessment against the final histological findings of the resected nodes and 95% Confidence interval (CIs) for FNRs will be calculated by exact method for the binomial proportion.

Ethical Considerations

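### Does the concordance outcome need a separate rule for a tattooed node that is palpable but neither hot nor blue?

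*Combined protocol and SAP*

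**What the plan says.** The protocol's only listed secondary outcome is the concordance rate between sentinel and tattooed nodes. Statistical Analysis repeats it without defining sentinel: "Concordance between the sentinel lymph nodes and tattooed biopsied lymph nodes will be reported".

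Study Procedure supplies the operational content:

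- On technique: "Sentinel lymph node biopsy will be performed in usual fashion including identification of palpable lymph nodes".
- On the comparison: "Correlation between, marked/tattooed and sentinel nodes (including palpable) will be determined".
- On recording: "Total number of sentinel lymph nodes retrieved, number of hot, number of blue and number of hot and blue will be documented".
- On overlap: "If the sentinel node is also the marked/tattooed node it will be assessed and documented".

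Study Design describes sentinel biopsy with two tracers and has the surgeon check, for the black ink, "is it easily distinguishable from methylene blue and is the tattooed lymph node also the SLN". It also has a second pathologist assess whether ink and methylene blue can be told apart, and sends sentinel and tattooed nodes in separately labelled containers. Study Setting, in justifying a single centre, mentions "subsequently retrieval of the SLN using dual tracer technique".

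**The concern.** Two readings of sentinel seem available. One is defined by tracer uptake, as the dual-tracer wording suggests. The other is everything removed at sentinel biopsy, palpable nodes included. The outcome line and the analysis sentence do not choose between them, and the words about palpable nodes are attached to a correlation rather than to the concordance rate.

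Under the wider reading, a tattooed node that is neither hot nor blue is concordant if it was felt and taken as sentinel. The wider rate can therefore only equal or exceed the tracer-only rate. Background motivates marking by a clip-and-seed study in which 25% of clipped nodes were not sentinel nodes and needed targeted retrieval to be found. A reader might want to know how many biopsied nodes tracer mapping alone would miss. If the tattooed node's own tracer status is not recorded at surgery, that cannot be reliably rebuilt later.

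**Working it through.** **The plan's own figure.** The plan gives no numerical target for concordance. Its sample size of 100 is for identification of the tattooed node at 93%. With n = z²p(1 − p)/d², z = 1.96, p = 0.93 and d = 0.05 (d is inferred; the plan does not state it), n = 100 to the nearest patient. Forty per cent of that is 40 = 10 + 30. Concordance plays no part in it.

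**Which definition the text gives.** Both Study Procedure sentences that mention palpable nodes place them inside sentinel biopsy. The Study Setting phrase explains why one centre is used; it does not define an outcome. The only text that addresses palpable nodes therefore counts them as sentinel. What is missing is a repetition of that in two other places.

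**How far the two rates can differ.** Let t be tracer-only concordance and q the share of tracer-negative tattooed nodes counted as sentinel because palpable. The wider rate is t + (1 − t)q, so the difference is (1 − t)q. Neither t nor q is in the documents. Assumed values with N = 40 (exact 95% intervals):

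| t | q | Tracer-only | Palpable included |
|---|---|---|---|
| 75% | 0 | 30/40 (58.8–87.3%) | 30/40 (58.8–87.3%) |
| 75% | 0.5 | 30/40 (58.8–87.3%) | 35/40 = 87.5% (73.2–95.8%) |
| 90% | 0.5 | 36/40 (76.3–97.2%) | 38/40 = 95.0% (83.1–99.4%) |

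N = 40 takes every tattooed node as retrieved. At the planned 93%, about 0.93 × 40 = 37 would be.

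**What the listed counts can recover.** Assume that the total T includes palpable-only nodes and that the hot (H) and blue (B) counts include nodes that are both (HB). Then tracer-positive nodes are U = H + B − HB, and tracer-negative sentinel nodes are T − U. For a patient whose tattooed node is recorded as sentinel:

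- T − U = 0: the tattooed node is tracer-positive.
- U = 0: it is palpable only.
- Both above zero: its tracer status is not fixed by the counts.

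Listing every possible (H, B, HB), the third case covers 0 of 4 patterns at T = 1, 3 of 10 at T = 2, 9 of 20 at T = 3 and 19 of 35 at T = 4. These are counts of patterns, not probabilities.

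**How far blue status narrows this.** Take T = 3, H = 2, B = 2, HB = 2. Then U = 2 and T − U = 1, so the counts alone are undecided. But every tracer-positive node here is blue, so the tattooed node's blue status settles it, provided the Study Design checks yield that status and ink and dye can be distinguished. With T = 3, H = 2, B = 1, HB = 1, U is again 2 and T − U is 1, but one node is hot only. If the tattooed node is not blue, it could be that node or the palpable-only one. The gap that remains is a non-blue tattooed node in a patient with both hot-only and tracer-negative sentinel nodes.

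**Bounds for the cohort.** With C concordant patients, k of them mixed (third case) and m with only tracer-negative sentinel nodes, tracer-only concordance lies between (C − k − m)/N and (C − m)/N. For C = 35, N = 40:

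- k = 5, m = 0: 30/40 to 35/40, or 75.0–87.5%.
- k = 10, m = 0: 25/40 to 35/40, or 62.5–87.5%.
- k = 5, m = 2: 28/40 to 33/40, or 70.0–82.5%.

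The values of C, k and m are illustrative.

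**The case for a change.** The best case for a change is that the tattooed node's gamma status exists only in theatre, costs one tick-box per node, and would answer the question that Background raises. Entry allows palpable nodes, so mixed patients are not ruled out. The plan also does not say whether hot and blue counts include dual nodes: T = 3, H = 1, B = 1, HB = 1 means two tracer-negative nodes if they do and none if they do not.

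Part of this stands. No gamma status of the tattooed node is listed, and the listed counts do not always recover tracer-only concordance.

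The rest does not make a defect. The plan never asks what tracer alone would miss. Background's worry is about nodes left behind without targeted retrieval, and a node felt and removed during sentinel biopsy is not left behind; the wider definition fits that worry at least as well. The operative form is not among the documents and may record more. If the total excludes palpable-only nodes, the overlap record is already tracer-only and nothing is lost. Entry by ultrasound alone, and surgery after chemotherapy in 30 of 40 patients, make q = 0 plausible.

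**Conclusion.** No change is needed. Palpable nodes are counted as sentinel in Study Procedure, and an analyst would carry that into the outcome line and the analysis sentence; leaving it out there is missing detail that the rest of the protocol supplies. The planned concordance rate is a legitimate description of sentinel biopsy as practised. A tracer-only line would be a supplementary analysis that some readers would like.

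Its distance from the planned rate is (1 − t)q: zero if q = 0, and 12.5 percentage points under the assumption t = 75%, q = 0.5. That compares with exact intervals spanning 30.9 points for 24/30 (61.4–92.3%) and 53.1 points for 8/10 (44.4–97.5%), illustrative results at the two phase sizes. This is a descriptive secondary outcome in a 40-patient pilot, with no test, stopping rule or treatment decision tied to it.

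The residual uncertainty about tracer status rests on T including palpable-only nodes and on H and B including dual nodes. How often it would arise cannot be determined from the documents.

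### Credentialing is offered as the control for assessor bias, but the plan does not mask the confirming pathologists to the surgeon's call, so the concordance check and the dye reading are unprotected

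*Combined protocol and SAP*

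**What the plan says.** All references are to the combined protocol and SAP.

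- **Control of assessor bias (Study Procedure).** Of using surgeons, radiologists and pathologists who are credentialed under institutional rules, the plan says that "this will lead to minimization of experimenter/assessor bias". The Strengths of Study bullet makes a similar appeal to training and credentials.
- **Specimen handling (Study Design, Phase I text).** "All lymph nodes excised including sentinel, tattooed (if recovered) and non-sentinel will be submitted in separately labelled containers".
- **Who decides concordance (Study Design).** The determination is "primarily done visually by the surgeon and confirmed by 2 independent pathologists, blinded to each other's findings".
- **The extra study reading (Study Design).** It consists of "evaluation of methylene blue and India Ink tattoo by the second independent study pathologist, to see if the two are grossly and/or microscopically distinguishable". The plan adds: "This additional evaluation will not affect the pathologic stage or further treatment decisions".
- **Outcomes (Study Objectives).** The primary outcomes are the surgeon's identification of the tattooed node during the operation, in each phase. The single secondary outcome is the concordance rate between sentinel and tattooed nodes.

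No section mentions coded specimens, mixed-order reading, or withholding the container category or operative findings from either pathologist.

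**The concern.** Every participant is injected with ink, so the surgeon expects to find it. That cannot be avoided. The protection has to come from the pathology check, and the plan describes that check as independent. It is independent only in one direction: each pathologist is kept from the other's findings, but nothing keeps either from the surgeon's. If the container tells the reader how the surgeon classified the node, the reader starts from the answer under test.

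The point has particular force here because methylene blue is injected in every patient, and the study asks whether it can be told apart from India ink. A reader who knows that a node was sent as tattooed, or as sentinel, has a strong hint about which dye to expect. At stake are the credibility of the concordance rate and the answer to the dye question. Treatment and staging are not affected.

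**Working it through.** This point is about masking, and the plan states no figure for it. The sample size of 100, and the 40 taken from it, are not affected. The check sets the provisions side by side and then gives two illustrations whose inputs are assumed.

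**Step 1. What each safeguard covers**

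| Provision | Where | Protects against | Leaves open |
|---|---|---|---|
| Credentialed staff | Study Procedure | Lack of skill | Knowledge of the surgeon's call |
| Pathologists blinded to each other | Study Design | One pathologist following the other | Both following the surgeon |
| Both pathologists examine all submitted nodes for ink | Study Procedure | Ink missed in nodes not called tattooed | Reading with the category known |
| Second pathologist compares the two dyes | Study Design | The dye question going unasked | The same |

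No row separates a pathologist from the surgeon's classification.

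**Step 2. Does the surgeon's call reach the pathologist?** Three categories are named and the containers are said to be separately labelled, so the natural reading is that the category shows on the container. The label wording is not given. The sentence sits in the Phase I description. The Phase II paragraph says the same procedure applies, but its parenthesis names only biopsy and tattooing. Carry-over is likely, not explicit.

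**Step 3. Which results are exposed?** Intraoperative visualisation is recorded before any specimen reaches pathology, and no rule makes it depend on confirmation. It is not exposed to this problem. The confirmed concordance rate and the India ink versus methylene blue reading are.

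**Step 4. Size in the proportion (assumed inputs).** The documents give no rate of wrong calls. Assume one call per patient and k wrong calls among 30 Phase II patients. The gap between the surgeon's proportion and a masked-confirmed proportion over all 30 is k/30:

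- k = 1: 1/30 = 3.3 points
- k = 2: 2/30 = 6.7 points
- k = 3: 3/30 = 10.0 points

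For example, 28/30 called is 93.3% (exact 95% CI 77.9 to 99.2). With two calls not confirmed, 26/30 is 86.7% (69.3 to 96.2).

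**Step 5. How following the label weakens the check (assumed inputs).** Let f be the share of wrong calls among 40 patients, 0.95 the chance that an unaided reader catches a wrong call, and a the share of cases in which the reader follows the label. Expected catches = 40 × f × 0.95 × (1 − a).

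- f = 10% (4 wrong calls), a = 0: 4 × 0.95 = 3.8
- f = 10%, a = 25%, 50%, 75%: 2.85, 1.9, 0.95
- f = 5% to 20%, a = 50%: 0.95 to 3.8, against 1.9 to 7.6 when a = 0

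The loss is proportional to a, a quantity that the present design cannot estimate.

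**The case against.** **The primary outcome is the surgeon's own observation.** This stands. A reader might infer that the main visualisation result is invalidated, or that masking a pathologist would repair it. The documents support neither: the planned proportion is what the surgeon sees, and it will be the same number after the change. The remedy adds a second proportion beside it.

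**The documents do not say that the readers see the surgeon's label.** This stands in part. They are silent on masking to the surgeon; they do not state that it is absent. The label text and its use in Phase II are inferred. Still, a plan that specifies blinding between pathologists and says nothing about blinding to the surgeon gives no assurance on the second.

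**Other safeguards exist.** True: two readers, all nodes examined for ink, microscopic inspection, and an explicit comparison of the dyes. A reader might infer that credentialing is the only safeguard; it is not. But none of the others removes knowledge of the call being confirmed.

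**The numbers are not decisive.** True. A reader might compare the 6.7-point shift with a 5-point planning margin. The Sample Size Assumption section states no margin; 5 points is only the half-width that happens to return 100. At n = 30 and 93%, the usual half-width is 1.96 × √(0.93 × 0.07 / 30) = 9.1 points, so such a shift lies within the pilot's own imprecision. The comparison should not be made.

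**Masking has practical limits.** Frozen section and the routine report need specimen identity, and masking the gross examination is harder than masking slides. The remedy should therefore be aimed at the slides.

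**Conclusion.** The concern holds in limited form. Credentialing does not make the pathologists independent of the surgeon, and the only blinding stated does not either. As written, the confirmation of sentinel/tattooed concordance and the reading of India ink against methylene blue are not protected from the surgeon's call.

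This rests on two inferences: that the container label carries the surgeon's category, and that the same handling applies in Phase II. The size cannot be taken from the documents; 3.3 to 10 points corresponds to an assumed 1 to 3 wrong calls in 30. The point does not alter the sample size, the primary proportion, staging or treatment. It is a worthwhile and inexpensive improvement to a reading already planned, and no reason to hold up the study.

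**What to change.** 1. Have the second study pathologist do the study dye reading, at least its microscopic part, on coded slides in mixed order, without the container category or operative note.
2. Record India ink and methylene blue as present or absent for each node before the code is broken.
3. Leave frozen section and the first pathologist's routine report unchanged.
4. In Statistical Analysis, report the surgeon's visualisation proportion as planned. Beside it, give the proportion of surgeon-called tattooed nodes in which the masked reader confirmed ink, with surgeon-reader agreement.
5. State that the procedure applies in both phases, and which pathologist's reading counts as the confirmation. Study Design gives the dye comparison to the second pathologist, while Study Design and Study Procedure elsewhere have both confirm.
6. Replace the credentialing sentence with this masking procedure.

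**Cost.** Slide coding, and a key held by existing study staff other than the reader. No new reader is needed, and by the plan's own statement the extra reading does not affect care. One limit remains: the masked reader can verify dye but not sentinel status established by gamma probe, so the concordance rate is only partly checked.
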